14. LIST OF TABLES

None.

15. LIST OF FIGURES

None.

[figure not shown]
ANNEX 1. LIST OF STAND ALONE DOCUMENTS

None.

ANNEX 2. ENCEPP CHECKLIST FOR STUDY PROTOCOLS

None.

PFIZER CONFIDENTIAL

ANNEX 3. ADDITIONAL INFORMATION

Appendix 1. WHO Classification of Myeloid Neoplasms and Acute Leukemia⁷²

WHO myeloid neoplasm and acute leukemia classification
Acute myeloid leukemia (AML) and related neoplasms
AML with recurrent genetic abnormalities
AML with t(8;21)(q22;q22.1); RUNX1-RUNX1T1
AML with inv(16)(p13.1q22) or t(16;16)(p13.1;q22); CBFB-MYH11
APL with t(15;17)(q22;q21); PML-RARA
AML with t(9;11)(p21.3;q23.3); MLLT3-KMT2A
AML with t(6;9)(p23;q34.1); DEK-NUP214
AML with inv(3)(q21.3q26.2) or t(3;3)(q21.3;q26.2); GATA2, MECOM
AML (megakaryoblastic) with t(1;22)(p13.3;q13.3); RBM15-MKL1
Provisional entity: AML with BCR-ABL1
AML with mutated NPM1
AML with biallelic mutations of CEBPA
Provisional entity: AML with mutated RUNX1
AML with myelodysplasia-related changes
Therapy-related myeloid neoplasms
AML, NOS
AML with minimal differentiation
AML without maturation
AML with maturation
Acute myelomonocytic leukemia
Acute monoblastic/monocytic leukemia
Pure erythroid leukemia
Acute megakaryoblastic leukemia
Acute basophilic leukemia
Acute panmyelosis with myelofibrosis
Myeloid sarcoma
Myeloid proliferations related to Down syndrome
Transient abnormal myelopoiesis (TAM)
Myeloid leukemia associated with Down syndrome
Blastic plasmacytoid dendritic cell neoplasm
Acute leukemias of ambiguous lineage
Acute undifferentiated leukemia
Mixed phenotype acute leukemia (MPAL) with t(9;22)(q34.1;q11.2); BCR-ABL1
MPAL with t(v;11q23.3); KMT2A rearranged
MPAL, B/myeloid, NOS
MPAL, T/myeloid, NOS
B-lymphoblastic leukemia/lymphoma
B-lymphoblastic leukemia/lymphoma, NOS

WHO myeloid neoplasm and acute leukemia classification
B-lymphoblastic leukemia/lymphoma with recurrent genetic abnormalities
B-lymphoblastic leukemia/lymphoma with t(9;22)(q34.1;q11.2); BCR-ABL1
B-lymphoblastic leukemia/lymphoma with t(v;11q23.3); KMT2A rearranged
B-lymphoblastic leukemia/lymphoma with t(12;21)(p13.2;q22.1); ETV6-RUNX1
B-lymphoblastic leukemia/lymphoma with hyperdiploidy
B-lymphoblastic leukemia/lymphoma with hypodiploidy
B-lymphoblastic leukemia/lymphoma with t(5;14)(q31.1;q32.3) IL3-IGH
B-lymphoblastic leukemia/lymphoma with t(1;19)(q23;p13.3); TCF3-PBX1
Provisional entity: B-lymphoblastic leukemia/lymphoma, BCR-ABL1-like
Provisional entity: B-lymphoblastic leukemia/lymphoma with iAMP21

Appendix 2. 2017 ELN Risk Stratification by Genetics in AML¹⁰

Risk category*	Genetic abnormality
Favorable	t(8;21)(q22;q22.1); RUNX1-RUNX1T1
	inv(16)(p13.1q22) or t(16;16)(p13.1;q22); CBFB-MYH11
	Mutated NPM1 without FLT3 -ITD or with FLT3 -ITD ^{low†}
	Biallelic mutated CEBPA
Intermediate	Mutated NPM1 and FLT3 -ITD ^{high†}
	Wild-type NPM1 without FLT3 -ITD or with FLT3 -ITD ^{low†} (without adverse-risk genetic lesions)
	t(9;11)(p21.3;q23.3); MLLT3-KMT2A ‡
	Cytogenetic abnormalities not classified as favorable or adverse
Adverse	t(6;9)(p23;q34.1); DEK-NUP214
	t(v;11q23.3); KMT2A rearranged
	t(9;22)(q34.1;q11.2); BCR-ABL1
	inv(3)(q21.3q26.2) or t(3;3)(q21.3;q26.2); GATA2,MECOM(EVII)
	-5 or del(5q); -7; -17/abn(17p)
	Complex karyotype,§ monosomal karyotype
	Wild-type NPM1 and FLT3 -ITD ^{high†}
	Mutated RUNX1 ¶
	Mutated ASXL1 ¶
	Mutated TP53 #

Frequencies, response rates, and outcome measures should be reported by risk category, and, if sufficient numbers are available, by specific genetic lesions indicated.

*Prognostic impact of a marker is treatment-dependent and may change with new therapies.

†Low, low allelic ratio (<0.5); high, high allelic ratio (≥0.5); semiquantitative assessment of *FLT3*-ITD allelic ratio (using DNA fragment analysis) is determined as ratio of the area under the curve “*FLT3*-ITD” divided by area under the curve “*FLT3*-wild type”; recent studies indicate that AML with *NPM1* mutation and *FLT3*-ITD low allelic ratio may also have a more favorable prognosis and patients should not routinely be assigned to allogeneic HCT.

‡The presence of t(9;11)(p21.3;q23.3) takes precedence over rare, concurrent adverse-risk gene mutations.

§Three or more unrelated chromosome abnormalities in the absence of 1 of the WHO-designated recurring translocations or inversions, that is, t(8;21), inv(16) or t(16;16), t(9;11), t(v;11)(v;q23.3), t(6;9), inv(3) or t(3;3); AML with *BCR-ABL1*.

||Defined by the presence of 1 single monosomy (excluding loss of X or Y) in association with at least 1 additional monosomy or structural chromosome abnormality (excluding core-binding factor AML).

¶These markers should not be used as an adverse prognostic marker if they co-occur with favorable-risk AML subtypes.

#*TP53* mutations are significantly associated with AML with complex and monosomal karyotype.

Appendix 3. Genetic Classification by Prognosis of B-cell Acute Lymphoblastic Leukemia⁷³

Good Prognosis	Intermediate Prognosis	Poor Prognosis	Undetermined Prognosis
Hyperdiploid karyotypes	t(1;19); TCF3-PBX1	Hypodiploid karyotypes	t(5;14); IL3-IGH*
t(12;21);ETV6-RUNX1 (TEL-AML1)		t(9;22); BCR-ABL	
		Philadelphia-like ALL	
		11q23 MLL rearrangements	

* t(5;14);IL3-IGH is a World Health Organization classified acute leukemia and prognosis data has not been determined.

Appendix 4. Response to Therapy will be Classified According to the International Working Group (IWG) Criteria 2003⁶⁹

Response Criterion	Neutrophils (microL)	Platelets (microl)	Bone Marrow Blasts (%)	Other
Early treatment	NA	NA	<5	
Morphologic leukemia-free state	NA	NA	<5	Flow cytometry EMD
Morphologic CR	>1,000	>100,000	<5	Transfusion EMD
Cytogenetic CR	>1,000	>100,000	<5	Cytogenetics - normal, EMD
Molecular CR	>1,000	>100,000	<5	Molecular - negative, EMD
Partial remission	>1,000	>100,000	>50 or decrease to 5-25	Blasts <5% if Auer rod positive

Abbreviations: CR, complete remission; EMD, extramedullary disease.

ALL	acute lymphoblastic leukemia
AML	acute myeloid leukemia
APL	acute promyelocytic leukemia
CNS	central nervous system
CR	complete remission; complete response
CRF	case report form
CRi	complete remission with incomplete hematological recovery or complete response with incomplete blood count recovery
ECOG	Eastern Cooperative Oncologic Group
EFS	event-free survival
ELN	European LeukemiaNet
EMA	European Medicines Agency
ICMJE	International Committee of Medical Journal Editors
IEC	independent ethics committees
IQR	interquartile range
IRB	institutional review board
KPS	Karnofsky performance status
LOYAL	Real-world Study in Acute Leukemia: Epidemiology, Treatment Patterns and Outcomes for B-cell ALL and AML in Adult Patients From Latin America
MDR-	complete remission without minimal residual disease
NIS	non-interventional study
OS	overall survival
PPPY	per patient per year
PR	partial remission
R/R	relapsed/refractory
RFS	relapse-free survival
SAP	statistical analysis plan
SD	standard deviation
TTNT	time to next treatment
WHO	World Health Organization

3. Responsible Parties

Name	Title	Affiliation	Contact
PPD	PPD – Pfizer Oncology Emerging Markets	Pfizer	PPD

Effective Date: 01Feb2022

PPD	PPD	Pfizer	PPD
PPD	Senior Consultant	IQVIA	PPD
PPD	Statistician	IQVIA	PPD
PPD	Associate Consultant	IQVIA	PPD

4. List of Amendments and Updates

Version Number	Date	Section of the SAP	Amendment or update	Reason	Major (Y/N)
1.0	18Apr 2022			Original (not applicable)	
2.0	09Dec 2022	Abbreviations, Team members, and Sections 5, 8.3.3, 8.7, 13.1.	Update	Test with 20% of the data entered in the CRF	N

5. Supporting Information

This statistical analysis plan (SAP) was developed in accordance with the study protocol Real-World Study in Acute Leukemia: Epidemiology, Treatment Patterns and Outcomes for B-Cell acute lymphoblastic leukemia (ALL) and acute myeloid leukemia (AML) in Adult Patients from Latin America – Loyal Study (protocol number X9001302).

This SAP was developed in accordance with the European Network of Centres for Pharmacoepidemiology and Pharmacovigilance Guide on Methodological Standards in Pharmacoepidemiology

6. Project Rationale and Background

To date there is scarce data on the epidemiology and treatment patterns of patients with acute leukemias in Latin America. Despite the various guidelines and recommendations for diagnosis, risk assessment, and therapy strategies most of them are not feasible in the clinical practice of a low/middle-income region. The lack of access to technologies for cytogenetic analysis and molecular profiling, besides the limit access to target therapies are important hurdles in the care of patients with AML and ALL.

There are guidelines developed by the Ministries of Health and the local hematology/oncology medical societies for ALL and AML in Brazil [1–4], Argentina [5], Colombia [6] e Chile [7–9]. However, the understanding of ALL and AML in the real-world context of developing countries is very limited. Progress in being made in the real-world setting, leading to improvements in the way the diseases are managed [10]. Therefore, this non-interventional study aims to describe the current epidemiology, treatment

patterns and health care resource use of adult patients diagnosed with B-cell ALL relapsed/refractory (R/R) and newly diagnosed (*de novo*) AML in four Latin American countries.

7. Research Questions and Objectives

The aim of this study is to describe the current epidemiology, treatment patterns, outcomes and healthcare resource use of adult patients diagnosed with B-cell ALL R/R and newly AML in four Latin American countries.

7.1. Primary Objective(s)

- To describe the clinical and demographics characteristics of newly diagnosed AML (and follow up treatment for R/R disease when available) and R/R B-cell ALL patients
- To assess treatment patterns in current practice of newly diagnosed AML and R/R B-cell ALL patients

7.2. Secondary Objective(s)

- To describe the cytogenetic and molecular profile of newly diagnosed AML and R/R B-cell ALL patients, when available
- To evaluate the risk stratification of newly diagnosed AML and R/R B-cell ALL patients
- To describe the clinically relevant events of newly diagnosed AML and R/R B-cell ALL patients
- To estimate event-free survival (EFS) of newly diagnosed AML and R/R B-cell ALL patients
- To assess patient response rate to treatment for newly diagnosed AML and R/R B-cell ALL patients
- To describe, for R/R B-cell ALL patients, treatment received when newly diagnosed for ALL (frontline B-cell ALL treatment)
- To estimate the overall survival (OS) and the 1, 3- and 5-year overall survival (OS) of newly diagnosed AML and R/R B-cell ALL patients
- To estimate relapse-free survival (RFS) for newly diagnosed AML patients
- To describe healthcare resource utilization of newly diagnosed AML and R/R B-cell ALL patients

8. Research Methods

8.1. Study Design

The current study is a retrospective multicenter non-interventional study using real-world data collected from medical records to describe the epidemiology of acute leukemias and treatment patterns among patients diagnosed with B-cell ALL R/R or AML in 4 Latin American countries: Argentina, Brazil, Chile, and Colombia. In addition, as secondary objectives, the study will also describe molecular profile, cytogenetic risk, clinical outcomes, and healthcare resource utilization of treated B-cell ALL R/R and AML patients.

All patients with newly diagnosed AML or with R/R B-cell ALL diagnosed between 01 January 2015 and 31 December 2019 will be included in the study for medical chart abstraction. Data on demographics, clinical characteristics, treatment regimens, among others will be collected. Healthcare resource utilization will be captured to understand the management pattern of both patient's population. All relevant data reported in the medical chart since diagnosis date (index date) until the study enrollment or death, whichever comes earlier, will be assessed.

8.2. Setting

8.2.1. Study Time Period

For this study, data from patients treated at public or private healthcare facilities in Argentina, Brazil, Chile, Colombia, diagnosed with R/R B-cell ALL or AML between 01 January 2015 and 31 December 2019 will be considered for the analysis.

The eligibility period of 5 years was determined to increase the overall patient representativeness, and to allow ample follow-up to assess survival outcomes.

The study will be conducted in approximately 15 sites distributed across Argentina, Brazil, Chile, and Colombia, and is expected to enroll approximately 700 patients with R/R B-cell ALL and AML in a consecutive matter. To assure the representativeness of each country, the number of sites and the total expected enrolled patients will be limited according to the country, considering the prevalence/incidence of the diseases.

Data collection will occur in a period of up to 12 months following the independent ethics committee (IEC)/ institutional review board (IRB) approval and study set up. Patients will be consecutively enrolled, considering both target population, with no set proportion of AML and R/R B-cell ALL patients to be included in the study. However, it is expected a higher proportion of AML patients in the cohort. The study period will comprise since diagnosis date (index date) until the study enrollment or death, whichever comes earlier.

[figure not shown]

Figure 1. Study time period.

8.2.2. Index Date

Date of first diagnosis of R/R B-cell ALL or newly AML.

8.2.3. Follow-up Period and Censoring

Patients will be followed in the cohort from the index date until the end of the study period or the patient's last information available in the databases.

8.2.4. Study Population Definitions

Patients diagnosed with R/R B-cell ALL or newly AML that received at least one line of treatment for R/R B-cell ALL or newly AML within the study period.

8.2.5. Patient Selection

8.2.5.1. Inclusion Criteria

Patients will be included in the study if they fit all of the following criteria:

- Patients with ≥ 18 years old at diagnosis
- Confirmed diagnosis of R/R B-cell ALL or newly diagnosed of AML between 01 January 2015 and 31 December 2019, as documented in the medical chart and according to the physician's notes
- Patients that received at least one line of treatment for R/R B-cell ALL or newly AML within the study period; for R/R B-cell ALL patients, data on previous therapy will also be collected if available.

8.2.5.2. Exclusion Criteria

Patients will be excluded from the study if they fit at least one of the following criteria:

- Patients with no medical chart available;
- Patients with unreliable data as per investigator's opinion (e.g. excessive missing data or inconsistency data)
- Patients that have participated in any interventional clinical trial for R/R B-cell ALL or AML at any moment. Patients under any compassionate use is allowed.
- Patients with secondary AML;
- Patients with any concomitant primary malignancy;
- Patients with acute promyelocytic leukemia (APL).

8.2.5.3. Selection of Comparator Patients

Not applicable

8.2.6. Sub-Population

Not applicable

8.3. Variables

8.3.1. Exposures

Patients will be considered to have been exposed if:

- at least one line of treatment for R/R B-cell ALL or newly AML within the study period

8.3.2. Outcomes

Primary outcomes

1. Description of demographic and clinical presentation characteristics at the moment of R/R B-cell ALL or AML diagnosis
2. Treatment description considering the front-line therapy and subsequent regimen(s) required for patients with R/R B-cell ALL and AML, including any systemic chemotherapy, target therapy, hematopoietic stem cell transplantation (autologous/allogenic), intrathecal chemotherapy and palliative management.

Secondary outcomes

3. Description of subtypes of AML and B-cell ALL based on the cytogenetic and molecular abnormalities, according to the WHO classification

Effective Date: 01Feb2022

4. Proportion of patients of each prognostic-risk group (favorable, intermediate, adverse) among newly diagnosed AML patients, based on cytogenetic profile
5. Description of the treatment standard from diagnosis to inclusion of R/R ALL patients
6. Description of clinically relevant events presented by AML and R/R B-cell ALL patients since treatment initiation until loss of follow-up or death from any cause;
7. The EFS will be the measure of time since diagnosis until failure to achieve complete remission (CR), or disease progression after CR, or death from any cause for both AML and R/R B-cell ALL patients;
8. The OS will be the measure of median time since diagnosis until death from any cause for both AML and R/R B-cell ALL patients;
9. The OS will also assess the proportion of AML and R/R B-cell ALL patients alive after 1, 3 and 5 years, if feasible, since treatment initiation;
10. For AML patients who achieved CR, the RFS will be the measure of time since the CR attainment until relapse or death from any cause;
11. For AML patients the response to induction and consolidation therapy will assess the proportion of patients who achieve CR, complete remission with incomplete hematological recovery (CRI), complete remission without minimal residual disease (MDR-), partial remission (PR), and progressive disease
12. For R/R B-cell ALL patients the response to the rescue treatment will access the proportion of patients with CR, complete remission without MRD-, PR, and progressive disease
13. Health care resource utilization description, considering the outpatient utilization, inpatient admissions, hospitalization length of stay, and concomitant medication prescription since diagnosis until the loss of follow-up or death from any cause.

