8.7. Data Analysis

Analyses will be descriptive in nature, as no hypothesis is being tested. Disease staging, comorbidities, demographic, clinical characteristics will be described at the date of diagnosis and/or treatment initiation for patients diagnosed with B-cell ALL R/R or AML. Treatment and clinical information will be assessed up to the most recent data available at the study enrollment. The treatments will be described in sequence according to the chronological order of administration. The duration through the number of cycles will be evaluated. Dose reduction information will also be collected. All analysis, including subgroup assessment, will be performed according to the data availability.

Continuous variables will be described as mean and standard deviation (SD), and/or as median, minimum, maximum, interquartile range (IQR, 25th and 75th percentiles). Categorical variables will be described by simple and cross contingency tabulation, with absolute frequencies and percentages. Missing values will be included in the denominators for the calculation of percentages and missing categories will be presented.

Follow-up period will be considered the time (in years) elapsed since B-cell ALL R/R or AML diagnosis until the study enrollment. It will be summarized as a continuous variable.

All time-to-event analysis will be described using Kaplan Meier methods and plots, if appropriate. The following definition and parameter analysis will be considered:

- Time to next treatment (TTNT) – considered as the time from the start date of the front-line therapy to the start date of a subsequent line of therapy. Patients without a subsequent line of therapy will be censored at study enrollment, last visit, last contact, or death, whichever comes first. It will be presented in months.
- Overall survival (OS) – considered as death from any cause from the time of initiation of diagnosis or treatment [12,13]. Patients not known to have died will be censored at study enrollment, last visit, last contact, whichever comes later. The median OS and, if feasible, the % of alive patients in 1, 3- and 5-years follow up of newly diagnosed AML and R/R B-cell ALL patients will be assessed.

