 - Hepatotoxicity.
- Most common adverse events description

7. To each newly AML and R/R B-cell ALL patients, the EFS will measure time since the date of initiation of treatment (or newly AML diagnosis and newly ALL diagnosis, if the previous is not available) until i) treatment end date (or treatment start date of the next treatment line, if the previous is not available) when treatment response was Refractory disease(5) or Relapsed from CR or CRI or recurrent disease(6); i) date of death, whichever comes first. This time-to-event analysis will be described summarized in tables and using Kaplan Meier methods and plot, if appropriate. Patients not known to have any of these events are censored on the date they were last examined:

newly AML

- Descriptive (median and CI(95%) estimations of Kaplan-Meier) of EFS;
- Time categorized count and percentages.

R/R B-cell ALL

- Descriptive (median and CI(95%) estimations of Kaplan-Meier) of time between treatment initiation and R/R event in months;

- Time categorized count and percentages.

8. The OS will be measure for both newly AML and R/R B-cell ALL patients as median time since newly diagnosis or treatment initiation until death from any cause. This time-to-event analysis will be described using a Kaplan Meier plot, if appropriate

newly AML

- Descriptive (median and CI(95%)) estimations of Kaplan-Meier) of time between date of diagnosis or treatment initiation and R/R event in months;
- Time categorized count and percentages.

This analysis will also be described for fit and non-fit newly AML patients.

R/R B-cell ALL

- Descriptive (median and CI(95%)) estimations of Kaplan-Meier) of OS;
- Time categorized count and percentages.

9. The median OS and the percentage (and 95% confidence intervals) of alive patients in 1, 3- and 5-years, if feasible, follow up of newly diagnosed or treatment initiation AML and R/R B-cell ALL patients will be assessed. The OS will be defined as median time since newly diagnosis or treatment initiation until death from any cause. This time-to-event analysis will be described using a Kaplan Meier plot, if appropriate.

newly AML

- Descriptive (median and CI(95%)) estimations of Kaplan-Meier) of time between treatment initiation and death in months;
- Time categorized count and percentages.

This analysis will also be described for fit and non-fit newly AML patients

R/R B-cell ALL

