- Descriptive (median and CI(95%)) estimations of Kaplan-Meier) of time between treatment initiation and death in months;
- Time categorized count and percentages.

10. For all AML patients who achieved Complete remission/response (CR) or Complete remission/response with incomplete hematological/count recovery (CRI) at the end of treatment, the RFS analysis will consider the treatment end date until date of next treatment initiation or date of death, whichever comes first. This time-to-event analysis will be described using a Kaplan Meier plot, if appropriate.

newly AML

- Descriptive (median and CI(95%)) estimations of Kaplan-Meier) of RFS
- Time categorized count and percentages.

11. For newly AML patients, each treatment response (induction and consolidation therapy) will assess the proportion of patients who achieve complete remission (CR), complete remission with incomplete haematological recovery (CRI), complete remission without minimal residual disease (MDR-), partial remission (PR), and progressive disease. No statistical testing will be carried out. Only descriptive data will be reported (absolute number, frequency, mean \pm standard deviation, median, interquartile range, minimum or maximum) for.

Newly AML patients:

- Treatment response
 - CR,
 - CRI,
 - partial remission/response,
 - progressive disease,
 - refractory disease,
 - relapsed from CR or CRI or recurrent disease,
 - other
- Minimal residual disease (MRD) evaluation for patients that achieved CR or CRI and the diagnose method for MRD evaluation
- Patient status description

12. For R/R B-cell ALL patients, each treatment response (to rescue treatment) will access the proportion of patients with complete remission (CR), complete remission without minimal residual disease (MRD-), partial remission (PR), and progressive disease. No statistical testing will be carried out. Only descriptive data will be reported (absolute number, frequency, mean ± standard deviation, median, interquartile range, minimum or maximum) for.

R/R B-cell ALL patients:

- Treatment response
 - CR,
 - CRI,
 - partial remission/response,
 - progressive disease,
 - refractory disease,
 - relapsed from CR or CRI or recurrent disease,
 - other
- minimal residual disease (MRD) evaluation for patients that achieved CR or CRI and the diagnose method for MRD evaluation
- Patient status description

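### The SAP gives overall survival and event-free survival more than one start date, leaves the R/R ALL fallback date unclear, and ends one OS output at the wrong event

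*SAP*

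**What the plan says.** **OS start.** SAP 8.3.2 item 8 reads: "The OS will be the measure of median time since diagnosis until death from any cause for both AML and R/R B-cell ALL patients". Item 9, directly below, takes the "proportion of AML and R/R B-cell ALL patients alive after 1, 3 and 5 years, if feasible, since treatment initiation". SAP 8.7 counts "death from any cause from the time of initiation of diagnosis or treatment [12,13"] and gives no rule for choosing between the two dates. SAP 8.7.2 items 8 and 9 keep the choice open, "as median time since newly diagnosis or treatment initiation until death from any cause", but the item 9 output bullets for both cohorts ask for the Kaplan-Meier median "of time between treatment initiation and death in months".

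**EFS start.** SAP 8.3.2 item 7 reads: "The EFS will be the measure of time since diagnosis until failure to achieve complete remission (CR"), with progression after remission and death as the further events. SAP 8.7.2 item 7 reads: "the EFS will measure time since the date of initiation of treatment (or newly AML diagnosis and newly ALL diagnosis", the bracketed dates applying only when the treatment date is unavailable). SAP 8.7 also starts EFS at treatment but states the fallback twice: first as an unspecified diagnosis date, then in the next sentence as the new AML or new ALL diagnosis.

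**OS end.** The AML bullet under the OS heading in SAP 8.7.2 item 8 asks for an estimate "of time between date of diagnosis or treatment initiation and R/R event in months".

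**Protocol.** Section 9.3.1.2 starts EFS, median OS and 1-, 3- and 5-year OS at treatment initiation. Section 9.7 starts EFS at treatment, but for OS it has the same open choice of diagnosis or treatment as SAP 8.7.

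**The concern.** A survival endpoint needs one origin, one fallback and one terminal event. Here the sections disagree, and the programmer would have to pick.

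- Under 8.3.2, median OS and the landmark percentages are on different clocks and cannot be read from one Kaplan-Meier curve. Under the 8.7.2 item 9 bullets they can.
- For EFS, the outcome list contradicts the operational rule.
- For R/R ALL patients without a treatment start date, one wording of the fallback may point to a date before the cohort's own index date, so these patients would be on a different clock from everyone else.
- The item 8 AML bullet, programmed as written, does not produce overall survival.

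Eligibility requires at least one line of treatment (SAP 8.2.5.1). With a diagnosis origin, the interval from diagnosis to treatment is therefore survival time that every included patient is guaranteed to have. The choice also carries into the EFS and OS subgroup tables (SAP 8.7.6) and the fit and non-fit AML tables (8.7.2 items 8 and 9).

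**Working it through.** **1. The definitions side by side**

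| Place | EFS start | OS start | OS end |
|---|---|---|---|
| Protocol 9.3.1.2 | treatment | treatment (median and 1/3/5-year) | death |
| Protocol 9.7 | treatment | diagnosis or treatment | death |
| SAP 8.3.2 items 7–9 | diagnosis | diagnosis (median); treatment (1/3/5-year) | death |
| SAP 8.7 | treatment, diagnosis as fallback | diagnosis or treatment | death |
| SAP 8.7.2 items 7–9, text | treatment, diagnosis as fallback | diagnosis or treatment | death |
| SAP 8.7.2 item 8, AML bullet | – | diagnosis or treatment | R/R event |
| SAP 8.7.2 item 9, bullets | – | treatment | death |

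For EFS this is a direct contradiction between 8.3.2 and the later sections. For OS, 8.3.2 is split within itself, while 8.7 and the 8.7.2 text leave the origin open.

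**2. The R/R ALL fallback.** The SAP index date (8.2.2) is the first diagnosis of R/R disease. SAP 8.7.2 item 5 uses the term for newly diagnosed B-cell ALL to mean treatment from the original ALL diagnosis onward. Read that way, the fallback lies before the index date. The reading is not certain, because 8.7.2 item 1 attaches the same adverb to R/R ALL. The direction of bias is also open: every R/R ALL patient has already relapsed or been refractory (protocol 9.2.3), that is itself an EFS event in SAP 8.7, and the SAP does not restrict the event search to R/R lines.

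**3. Size of the OS origin choice.** The documents give no median, gap or missing-date rate, so all inputs are assumed. Take exponential survival from treatment, S(t) = 2^(−t/m), median m = 6, 9 or 12 months, and a gap g from diagnosis to treatment of 7 to 30 days (7/30.44 = 0.23 to 30/30.44 = 0.99 month).

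- The median rises by g: 0.2 to 1.0 month.
- OS at T rises by 2^(−(T−g)/m) − 2^(−T/m). At 12 months the smallest value (m = 12, g = 0.23) is 0.67 points and the largest (m = 9, g = 0.99) is 3.13 points. At 36 months the range is 0.04 to 0.73 points, and at 60 months 0.00 to 0.18 points.
- For scale, the 95% half-width is 1.96·√(s(1−s)/n), without censoring. With an assumed 600 AML and 100 R/R ALL patients out of 700 and s from 0.25 to 0.50, it is 3.5 to 4.0 points and 8.5 to 9.8 points.

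**4. Size of the fallback.** Assume a true EFS median of m = 4 months from R/R treatment, an original diagnosis 12 months before that, and a share p of missing start dates. True 1-year EFS is 2^(−12/4) = 12.5%.

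| p | Only R/R-line events counted: (1−p)·0.125 + p | Qualifying event counted, before month 12: (1−p)·0.125 |
|---|---|---|
| 1% | 13.4% | 12.4% |
| 5% | 16.9% | 11.9% |
| 10% | 21.3% | 11.3% |

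Over m = 3 to 6 months, gaps of 6 to 24 months and p = 1% to 10%, the change is +0.2 to +9.4 points in the first case (for gaps under 12 months the last term becomes p·2^(−(12−gap)/m)) and −0.1 to −2.5 points in the second. If the qualifying event counts but falls after month 12, the change is p·(1−2^(−12/m)), or +0.8 to +9.4 points.

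**The case against.** Five points can be made for the plan.

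- **The OS ambiguity is inherited.** Protocol 9.7 carries the same open wording that SAP 8.7 repeats. This is true and should be acknowledged, but it explains the problem without resolving it. The SAP is where it should be settled.
- **Either origin would do if used consistently, and the index date and follow-up (SAP 8.2.2, 8.2.3) start at diagnosis.** This has some force. Treatment start is still the better choice: protocol 9.3.1.2 uses it for every OS and EFS measure, protocol 9.7 uses it for EFS, and treated-only entry makes time before treatment guaranteed survival.
- **EFS is settled in the operational text.** SAP 8.7 and 8.7.2 agree on treatment start, and the SAP's update list shows 8.7 as revised in version 2.0 without listing 8.3.2. Item 7 of 8.3.2 is then an outlier needing a short correction. That is fair for the origin, but the fallback stays unclear within 8.7 itself.
- **The fallback reading is uncertain and few patients would use it.** Both are accepted. All patients were treated, so missing start dates are probably rare. The date is nevertheless not defined under either reading.
- **The R/R event bullet is a slip.** Very likely: the item's lead sentence and the item 9 bullets say death, and the R/R ALL EFS bullet in item 7 has the same R/R event wording. It still needs correcting. The table shells named in SAP 13.1 are a separate workbook that was not available, so whether they carry the slip could not be checked.

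**Conclusion.** The concern holds in all four parts, with the R/R ALL fallback the least certain in its reading. The SAP states contradictory rules for the EFS and OS origin, does not identify the fallback date for R/R ALL, and ends one AML OS output at the wrong event.

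The numerical effect of the OS origin is modest: under the assumptions above, at most about 3 points at 1 year, below the assumed half-widths, and under 1 point at 3 and 5 years. The fallback shifts 1-year EFS by about +0.9 or −0.1 point at 1% missing start dates in the central case. It could matter more at 5% to 10% missing, in a direction the SAP does not fix. The item 8 bullet changes the endpoint itself, whatever the gap.

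Because these are secondary descriptive endpoints, this is a should-fix. Confidence is high that the text conflicts; the sizes rest wholly on assumed medians, gaps, missing rates and exponential survival.

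**What to change.** In the SAP:

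1. Use one origin for OS and EFS in 8.3.2 items 7–9, 8.7 and 8.7.2 items 7–9: start of first AML treatment, or start of first treatment for R/R B-cell ALL.
2. If that date is missing, fall back to the 8.2.2 index date (AML or R/R diagnosis), never the original ALL diagnosis. Count only events after the origin, and report how many patients used the fallback.
3. Read the median and the 1-, 3- and 5-year OS from the same Kaplan-Meier curve.
4. In the AML bullet of 8.7.2 item 8, replace the R/R event with death, and check the table shells for the same slip.

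The cost is wording and programming edits on dates already collected. Protocol 9.7 lets the SAP modify the plan and reserves amendment for major changes to primary endpoints, so no protocol amendment is needed. OS figures will be slightly lower than on a diagnosis clock; R/R ALL EFS could move either way.
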